10.2.7 Important Protocol Deviations

An important protocol deviation (IPD) is a deviation that may significantly affect the completeness, accuracy, or reliability of the study data or that may significantly affect a subject's rights, safety, or well-being. IPD rules will be developed and finalized before the data lock for Part A.

Protocol deviations that should be considered as potential IPDs include, but are not limited to:

- Subject was enrolled in the study despite not satisfying one or more inclusion/exclusion criterion
- Subject was less than 80% compliant with study drug for non-safety reasons
- Subject received prohibited concomitant medications

- Subject received the wrong treatment or incorrect doses
- Subject remained in the study despite meeting withdrawal criteria

The occurrence of any of these events should be considered as a potential IPD, but the team should categorize such an event as an IPD only if it has the potential to affect the completeness, accuracy, or reliability of the study data or the subject's rights, safety, or well-being.

An individual subject data listing and a summary table of IPDs based on the FAS will also be provided.

10.3 Safety Analysis

The primary objective of Study 116 Part A is to evaluate the long-term safety and tolerability of TEZ/IVA. The overall safety profile of study drug will be assessed in terms of the following safety and tolerability endpoints:

- Treatment-emergent adverse events (TEAEs)
- Clinical laboratory values
- Standard 12-lead ECGs
- Vital signs
- Pulse oximetry
- Ophthalmologic examination

Analysis of AEs will be based on events that occur during the TE period of the Part A, for all subjects in the Safety Set. Pooled AE data from Study 113 Part B and Study 115 (only those who received TEZ/IVA) will be displayed side-by-side with AE data from Study 116 Part A. When displayed side-by-side with parent study results, exposure-adjusted rates will be provided.

Other safety analyses will be based on data from the TE period for all subjects in the Safety Set; and will be presented overall. The Safety Set will be used for all listings unless otherwise specified.

Baseline value will be used to calculate change from baseline for continuous safety endpoints.

Only descriptive summaries will be presented, and no statistical testing is planned.

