2 PROTOCOL SYNOPSIS

Title A Phase 3, Open-label, Rollover Study to Evaluate the Safety and Efficacy of Long-term Treatment With Tezacaftor in Combination With Ivacaftor in Subjects With Cystic Fibrosis Aged 6 Years and Older, Homozygous or Heterozygous for the *F508del-CFTR* Mutation

Brief Title A Study to Evaluate the Safety and Efficacy of Long-term Treatment With TEZ/IVA in CF Subjects With an *F508del-CFTR* Mutation

Clinical Phase and Clinical Study Type Phase 3, safety and efficacy

Objectives Primary Objective

To evaluate the long-term safety and tolerability of tezacaftor in combination with ivacaftor (TEZ/IVA) in subjects with cystic fibrosis (CF) aged 6 years and older, homozygous or heterozygous for the *F508del* mutation

Secondary Objective

[figure not shown]
To evaluate the long-term efficacy of TEZ/IVA in subjects with CF aged 6 years and older, homozygous or heterozygous for the *F508del* mutation

[figure not shown]
Endpoints Primary Endpoint

Safety and tolerability of long-term TEZ/IVA treatment based on adverse events (AEs), clinical laboratory values (serum chemistry, hematology, lipids, and vitamins), standard 12-lead ECGs, physical examinations (PEs), vital signs, ophthalmologic examinations, and pulse oximetry

Secondary Endpoints

- Absolute change from baseline in lung clearance index_{2.5} (LCI_{2.5}; for subjects from Study VX16-661-115 [Study 115] and the Study VX15-661-113 Part B [Study 113B] LCI Substudy only)
- Absolute change from baseline in sweat chloride
- Absolute change from baseline in Cystic Fibrosis Questionnaire–Revised (CFQ-R) respiratory domain score
- Absolute change from baseline in body mass index (BMI)

Number of Subjects Study VX17-661-116 is a rollover study. Approximately 56 subjects from Study 113B and 65 subjects from Study 115 are potentially eligible for enrollment. Up to approximately 121 subjects are potentially eligible for enrollment.

Study Population Male and female subjects with CF aged 6 years and older, who completed Study 113 B or Study 115 and are

- homozygous for *F508del* (F/F),
- heterozygous for *F508del* and a second allele with a residual CFTR-function mutation (F/RF), or
- heterozygous for *F508del* and a second allele that has been shown to be responsive to TEZ/IVA

Investigational Drug **Active substance:** TEZ and IVA
Activity: CFTR corrector and potentiator (increased Cl⁻ secretion)

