8.1 Inclusion Criteria

1. Subject's legally appointed and authorized representative will sign and date an informed consent form (ICF) and the subject will sign an assent form (if applicable).
2. Willing and able to comply with scheduled visits, treatment plan, study restrictions, laboratory tests, contraceptive guidelines, and other study procedures.
3. Completed the Week 24 Visit in Study 113B or the Week 8 Visit in Study 115.

Added guidance:

- Subjects who had a study drug interruption at the last scheduled visit of Study 113B or Study 115, subjects who required study drug interruption that was to be continued or initiated at Day 1 in Study 116, or subjects who resumed study drug in the parent study after a study drug interruption due to elevated transaminases, but who did not complete at least 4 weeks of rechallenge with study drug (due to the timing of the rechallenge versus the time remaining in the parent study), must receive approval from the Vertex medical monitor.

Note: Subjects who permanently discontinue study drug treatment during the parent study, including at the last visit of the Treatment Period, are not eligible.

4. Did not withdraw consent from the parent study.
5. Subjects must have a genotype listed in [Appendix 1: CFTR Mutations](#). Note: Additional mutations may be evaluated and updates to the list of eligible mutations will be communicated to investigative sites through a memorandum. If TEZ/IVA receives marketing authorization for additional mutations in any country/region for patients ≥ 12 years old, a memorandum will be sent to investigative sites in that country/region and the newly approved mutations will also be eligible.
6. Willing to remain on a stable CF medication regimen through the Safety Follow-up Visit.

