9.1.1 Treatment Period

Treatment Period assessments are listed in [Table 3-1](#).

The Day 1 Visit of Study 116 will be on the **same day** as the last scheduled visit of the parent study; this will occur at the Week 24 Visit for subjects from Study 113B and at the Week 8 Visit for subjects from Study 115. Subjects will NOT have to repeat any Study 116 Day 1 Visit assessments that were specified to be performed at the last scheduled visit in the parent study.

Subjects who were enrolled in Study 116, but had Day 1 study drug administration procedures delayed (e.g., due to an AE), will repeat the safety, LCI (if applicable), [REDACTED] assessments that were specified to be performed at the Day 1 Visit before receiving their first dose of study drug.

For subjects at Study 116 sites that have NOT been activated by the time the subject has completed the last scheduled visit in the parent study, the Day 1 Visit of Study 116 will NOT coincide with the last scheduled visit of the parent study. Subjects at these sites with delayed activation will have to repeat any Study 116 Day 1 assessments that were specified to be performed at the last scheduled visit in the parent study.

All subjects will have study visits on Day 1 and at Weeks 12, 24, 36, 48, 60, 72, 84, and 96.

Study Visits on Day 15 and Week 4 are only required for subjects from Study 115.

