7 STUDY DESIGN

7.1 Overall Design

Study 116 is a Phase 3, multicenter, open-label, 2-part, rollover study in subjects with CF aged 6 years and older, who are homozygous or heterozygous for *F508del* and who completed the Week 24 Visit in Study 113 Part B or the Week 8 Visit in Study 115. A schematic of the study design is shown in Figure 7-1.

Figure 7-1 VX17-661-116 Study Design

Note: Subjects ≥12 years old will receive TEZ 100 mg qd/IVA 150 mg q12h regardless of weight (in Part A and Part B).

IVA: ivacaftor, q12h: every 12 hours, qd: daily, TEZ: tezacaftor

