7.2 Sample Size and Power

Study 116 Part A enrolled subjects from Study 113 Part B and Study 115. No formal sample size calculations were performed. Approximately 56 subjects from Study 113 Part B and approximately 65 subjects from Study 115 were potentially eligible for enrollment.

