10.4 Efficacy Analysis

All efficacy analyses described in this section will be performed by parent study based on the FAS (115/116 FAS and 113B/116 FAS) unless specified otherwise. LCI analysis will be based on the 115/116 FAS and the 113B/116 LCI FAS.

The analysis will include all available measurements during the efficacy analysis period.

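### The side-by-side AE display weights Studies 113B and 115 differently in its parent and Part A columns, so any difference in AE rate between the cohorts could be misread as a change with longer treatment

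*SAP*

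**What the plan says.** SAP 10.3 bases the AE analysis on treatment-emergent events in Part A for the whole Safety Set. For context it adds that "Pooled AE data from Study 113 Part B and Study 115 (only those who received TEZ/IVA) will be displayed side-by-side with AE data" from Part A, and it promises exposure-adjusted rates whenever that display is used. SAP 10.3.1.1 to 10.3.1.4 list the overview, the SOC and PT summaries, the PT summaries and the events of special interest. None is split by parent study, and no stratified or standardised rate is described. Protocol 12.3.4.1 calls for AE tables overall and by treatment group, but SAP 7.3 describes a single treatment arm, so that wording does not supply the split.

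Elsewhere the SAP does separate the cohorts. For efficacy, "All efficacy analyses described in this section will be performed by parent study" (SAP 10.4). Demographics, medical history, medications and compliance (SAP 10.2.2, 10.2.3, 10.2.4 and 10.2.6) are shown for each parent-study subset and overall.

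On size and duration, SAP 7.2 says that "Approximately 56 subjects from Study 113 Part B and approximately 65 subjects from Study 115 were potentially eligible for enrollment", and SAP 7.1 describes subjects "who completed the Week 24 Visit in Study 113 Part B or the Week 8 Visit in Study 115". SAP section 4 gives 96 weeks of treatment in Part A for both cohorts.

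**The concern.** Exposure adjustment corrects for how long subjects are followed. It does not correct for which subjects supply the follow-up. In the parent column a Study 113B child contributes up to 24 weeks and a Study 115 child up to 8. In Part A both contribute up to 96, and Study 115 is the larger cohort. The two columns therefore average the cohorts with different weights.

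The columns also differ in membership. The parent column takes only the Study 115 children who received TEZ/IVA, while the Part A column takes every treated child. SAP 10.2.2 provides for subjects whose first TEZ/IVA dose falls in Part A, so that column mixes first-exposure time with continued-exposure time.

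In the SAP text available, this is the only planned comparison of longer-term with shorter-term AE rates, and long-term safety is the primary objective. A reader will naturally take a higher or lower Part A rate as a trend with time on drug. A shift in cohort mix can create such a pattern or hide one.

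**Working it through.** **Inputs.** Eligible subjects: about 56 (Study 113B) and 65 (Study 115), from Protocol section 2 and SAP 7.2. Treatment weeks: 24 and 8 in the parent studies (Protocol 8.1, SAP 7.1), and 96 in Part A (SAP section 4). The number of Study 115 children who received TEZ/IVA is not in the documents. I assume 65 as the maximum and 33 (about half) as a low value.

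**The documents' own figure.** 56 + 65 = 121, matching the synopsis: "Up to approximately 121 subjects are potentially eligible for enrollment". No person-time shares are stated.

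**Study 113B share of the parent column** = (56 × weeks) / (56 × weeks + n × weeks), where n is the number of Study 115 TEZ/IVA recipients.
- On-drug time, n = 65: 1344 / (1344 + 520) = 72.1%
- On-drug time, n = 33: 1344 / (1344 + 264) = 83.6%
- The SAP does not define the rate's denominator. Adding 28 days (4 weeks) per parent-study subject, n = 65: 56 × 28 / (56 × 28 + 65 × 12) = 1568 / 2348 = 66.8%

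**Study 113B share of the Part A column.**
- Full enrolment, equal follow-up: 5376 / (5376 + 6240) = 56/121 = 46.3%
- 80–100% of each cohort enrolling: 44.8 / 109.8 = 40.8% to 56 / 108 = 51.9%
- Mean follow-up of 60 to 96 weeks, differing by cohort: 3360 / (3360 + 6240) = 35.0% to 5376 / (5376 + 3900) = 58.0%

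**Apparent Part A/parent rate ratio when each cohort's rate is constant over time.** Let r be the Study 115:113B rate ratio, s_A the Part A share and s_P the parent share. Then

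ratio = [s_A + (1 − s_A)r] / [s_P + (1 − s_P)r]

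At s_A = 46.3%:

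| Parent share s_P | r = 0.5 | r = 1 | r = 1.5 | r = 2 |
|---|---|---|---|---|
| 66.8% (65 subjects, 28 days added) | 0.88 | 1.00 | 1.09 | 1.15 |
| 72.1% (65 subjects, on drug) | 0.85 | 1.00 | 1.11 | 1.20 |
| 83.6% (33 subjects, on drug) | 0.80 | 1.00 | 1.17 | 1.32 |

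Example: r = 2, s_P = 72.1% gives (0.463 + 1.074) / (0.721 + 0.558) = 1.537 / 1.279 = 1.20.

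Extremes for r = 2:
- Closest shares (66.8% versus 58.0%): 1.420 / 1.332 = 1.07
- Most distant shares (83.6% versus 35.0%): 1.650 / 1.164 = 1.42

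**After the split.** If each cohort is set beside itself, the ratio is 1.00 whenever that cohort's rate is constant, for any r.

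**Person-time in the smallest new column.** Study 115 parent period: 264 × 7 / 365.25 = 5.1 patient-years (33 subjects) to 520 × 7 / 365.25 = 10.0 (65 subjects). One event moves a rate there by about 0.20 to 0.10 per patient-year.

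**The case against.** The strongest reply is that the artefact is conditional. It needs AE rates that differ between the cohorts, and the documents report none. Both parent studies took children aged 6 to 11 at Screening with at least one *F508del* allele (Protocol 5.2), and the Part A dosing rules are common to both. If the rates are similar, the mismatch does nothing. This stands: rate ratios of 1.5 or 2 are scenarios, not forecasts.

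The display is also descriptive, with no testing. The Part A rates themselves are unaffected, and only their comparison with the parent column is at issue. That limits the importance but does not remove it, because with no test the reader interprets the two columns directly.

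Three stronger readings are tempting but not supported:
- *That 72% is a minimum for the Study 113B parent share.* The counts are approximate numbers eligible to roll over, not the treated parent populations that SAP 10.3 pools, and the denominator is undefined. The 46% likewise assumes full enrolment and equal follow-up, yet Protocol 9.9 allows children to leave for commercial drug or on genotype grounds.
- *That the SAP regards the cohorts as unsuitable for pooling.* SAP 10.4 only says that efficacy is analysed by parent study. SAP 10.4.2 ties the extra Study 115 covariates to consistency with the parent models, and baseline data are shown overall as well.
- *That the Study 115 visit schedule makes a rate difference likely.* It is true that "Study Visits on Day 15 and Week 4 are only required for subjects from Study 115" and that AEs are queried at every visit (Protocol 13.1.1.3). But AEs are collected continuously from consent, and two early visits in 96 weeks are weak evidence.

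Finally, a split comparison is still before-versus-after in growing children who completed a parent study. It removes the cohort-mix artefact but does not isolate time on drug.

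**Conclusion.** The point holds in conditional form. As planned, the two columns weight the cohorts differently, and nothing in SAP 10.3 to 10.3.1.4 corrects for it. The direction of the imbalance is firm: across the scenarios examined, the Study 113B share of the parent column (67–84%) exceeds its share of Part A (35–58%, centrally 46%). The size of any distortion is not firm. It is zero if the cohorts' rates are equal. For a twofold rate ratio in on-drug time it is about 1.20 to 1.32 at a 46% Part A share, and about 1.07 where the shares are closest. It reverses direction if Study 115 has the lower rate.

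These figures rest on approximate eligible counts, planned durations, an assumed range of 33 to 65 Study 115 TEZ/IVA recipients, and constant rates within each cohort. They apply to exposure-adjusted event rates. Percentages of subjects are weighted by heads and are affected mainly by the unequal 8, 24 and 96 week durations. This is an inexpensive improvement to interpretation, not an error that invalidates the safety analysis.

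**What to change.** In SAP 10.3, keep the pooled side-by-side display. In the overview and main exposure-adjusted side-by-side TEAE summaries, add five columns:
- Study 113B: parent period, and Part A
- Study 115 TEZ/IVA arm: parent period, and Part A
- Study 115 children first given TEZ/IVA in Part A: Part A only

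Add a statement that the pooled columns differ in cohort mix and should not be read alone as a trend with time on drug.

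The parent-study subsets are already used elsewhere in the SAP, the Study 115 TEZ/IVA group is already identified for the efficacy models, and SAP 10.1 already integrates the parent data, so no new data are needed. The cost is wider tables in more than one output, and unstable rates for rare preferred terms in the Study 115 parent column, which holds only about 5 to 10 patient-years. Keeping the pooled columns preserves the larger counts for those terms and leaves no treated child out of the display.

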8.2 Exclusion Criteria

1. History of any comorbidity that, in the opinion of the investigator, might confound the results of the study or pose an additional risk in administering study drug to the subject.

[figure not shown]
For example, history of cirrhosis with portal hypertension, and/or history of risk factors for Torsade de Pointes (e.g., familial long QT syndrome, hypokalemia, heart failure, left ventricular hypertrophy, bradycardia, myocardial infarction, cardiomyopathy, history of arrhythmia [ventricular and atrial fibrillation], obesity, acute neurologic events [subarachnoid hemorrhage, intracranial hemorrhage, cerebrovascular accident, and intracranial trauma], and autonomic neuropathy).

2. Pregnant and nursing females. Females of childbearing potential must have a negative pregnancy test at the Day 1 Visit before receiving the first dose of study drug (Section 11.4.2).
3. Sexually active subjects of reproductive potential who are not willing to follow the contraception requirements outlined in Section 11.4.8.
4. History of drug intolerance in the parent study that would pose an additional risk to the subject in the opinion of the investigator, and which should be discussed with the Vertex medical monitor. Examples of subjects who may not be eligible for the study include (but are not limited to) the following:
 - Subjects with a history of allergy or hypersensitivity to the study drug
 - Liver function test (LFT) abnormality during study drug treatment in the parent study or other qualified Vertex study that required permanent study drug discontinuation
 - Other severe or life-threatening reactions to the study drug in the previous study
5. History of poor compliance with study drug and/or procedures in a previous study as deemed by the investigator.
6. Ongoing participation in another study with investigational drug. Ongoing participation in a non-interventional study (including observational studies) is permitted. During the Treatment Period, subjects may screen for another Vertex-sponsored study of CFTR modulators, excluding studies of IVA monotherapy and lumacaftor in combination with IVA. If a subject chooses to enroll in the other Vertex-sponsored study, they will be terminated from Study 116 and will not be allowed to re-enroll in Study 116.

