8 ANALYSIS SETS

The following analysis sets are defined for Study 116 Part A: All Subjects Set, Safety Set, Full Analysis Set, 113B/116 Full Analysis Set, 115/116 Full Analysis Set, and 113B/116 LCI Full Analysis Set.

Enrolled subjects are those who signed a consent/assent form and had an enrollment date in the CRF for Part A.

All Subjects Set

The **All Subjects Set** will be defined as all subjects who were enrolled in Study 116 Part A or received at least 1 dose of TEZ/IVA in Study 116 Part A. This analysis set will be used for all individual subject data listings and the disposition summary table, unless specified otherwise.

Full Analysis Set (FAS)

The **Full Analysis Set (FAS)** will be defined as all subjects who were enrolled in Study 116 Part A, who received at least 1 dose of TEZ/IVA in Study 116 Part A and have an eligible genotype. The FAS will be used for efficacy analyses, unless otherwise specified.

115/116 Full Analysis Set (FAS), 113B/116 FAS and 113B LCI/116 FAS

The 115/116 FAS will be defined as the subset of FAS who were enrolled in parent Study 115. The 113B/116 FAS will be defined as the subset of FAS who were enrolled in parent Study 113B. The 113B/116 LCI FAS will be defined as the subset of Study 113B subjects who participated in the LCI sub-study in Study 113B.

Safety Set

The **Safety Set** will be defined as all subjects who are enrolled in study 116 Part A and who received at least 1 dose of TEZ/IVA in Study 116 Part A. The Safety Set will be used for all safety analyses, unless otherwise specified.

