10.2.5 Study Drug Exposure

Duration of study drug exposure (in days) will be calculated as: last dose date – first dose date + 1 day, regardless of study drug interruption. The first and last dose dates of Study 116 Part A will be used for the calculation.

Study drug exposure will be summarized descriptively by the number of subjects (n), mean, SD, median, min, and max based on the 116A Safety Set. It will also be summarized into the following categories: >0 to ≤12 weeks, >12 to ≤24 weeks, >24 to ≤36 weeks, >36 to ≤48 weeks, >48 to ≤60 weeks, >60 to ≤72 weeks, >72 to ≤84 weeks, >84 to ≤96 weeks, >96 weeks, using counts and percentages.

Additionally, the total study drug exposure, defined as the sum of the study drug exposure across all subjects (in patient-years), will be provided.

Exposure summaries will be based on the Safety Set.

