10.3.1.3 TEAEs and SAEs by PT

The number and percentage of subjects with TEAEs and SAEs will be summarized by PT. Exposure adjusted event rates may also be provided. When summarizing the number and percentage of subjects with an event, multiple occurrences of the same adverse event or a continuing adverse event for the same subject will be counted once. While summarizing the number of events for the exposure adjusted event rate, all occurrences will be counted.

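### The side-by-side AE table compares different populations, so a difference in rates between the parent studies and Study 116 cannot be read as change over time

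*SAP*

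**What the plan says.** SAP 10.3 bases the AE analysis on the Safety Set over the treatment-emergent (TE) period and then brings in the parent studies: AEs pooled over Study 113B and "Study 115 (only those who received TEZ/IVA) will be displayed side-by-side with AE data from Study 116 Part A". The measure follows: "When displayed side-by-side with parent study results, exposure-adjusted rates will be provided". For such rates SAP 10.3.1.3 adds: "While summarizing the number of events for the exposure adjusted event rate, all occurrences will be counted". Other safety analyses are shown overall, so this is the only planned safety contrast between the parent studies and long-term treatment.

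The Study 116 column is the Safety Set, which SAP 8 defines as "all subjects who are enrolled in study 116 Part A and who received at least 1 dose of TEZ/IVA in Study 116 Part A". Entry to it is filtered. Protocol 8.1 requires completion of the Week 24 Visit (Study 113B) or the Week 8 Visit (Study 115) and notes: "Subjects who permanently discontinue study drug treatment during the parent study, including at the last visit of the Treatment Period, are not eligible". Protocol 8.2 excludes "History of drug intolerance in the parent study that would pose an additional risk to the subject in the opinion of the investigator", and also subjects whom the investigator considers poorly compliant in a previous study.

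SAP 10.2.2 provides for subjects whose first TEZ/IVA dose falls in Study 116, and SAP 10.4.2.1 implies that Study 115 had a group not randomized to TEZ/IVA. SAP 10.3 does not separate these subjects in the AE display.

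On person-time, SAP 10.2.5 defines exposure in dosing days and says that "the total study drug exposure, defined as the sum of the study drug exposure across all subjects (in patient-years), will be provided". SAP 9.1 lets the TE period run up to 28 days past the last dose. The SAP does not say which of the two is the denominator for the AE rates.

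**The concern.** Two columns of rates with the same label invite the reader to compare them and call the difference an effect of longer treatment. Here the people change between the columns as well as the time on drug. Those who stopped TEZ/IVA for good in a parent study count on the left and cannot count on the right. Long-term safety is the primary objective, the display is descriptive, and no model, sensitivity analysis or caveat separates selection from time. The rows most exposed are AEs leading to discontinuation or interruption and transaminase events, because these lie closest to the reasons for which a subject would not roll over. Nor can a reader judge the size of the problem, since SAP 10.3 plans no count of parent TEZ/IVA subjects who did not enter Study 116.

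**Working it through.** **Figure in the documents.** 56 (Study 113B) + 65 (Study 115) = 121 potentially eligible, as the protocol synopsis states. The documents give no expected AE rate, no number treated with TEZ/IVA in the parent studies and no number who did not roll over, so every size below is an assumption shown as a range.

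**Step 1: selection alone.** Let d be the share of parent TEZ/IVA subjects who did not roll over, k their AE rate relative to the rest, and f their parent follow-up relative to the rest. Hold each child's rate constant. Then

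all-parent rate / rollover subjects' parent rate = [(1−d) + d·f·k] / [(1−d) + d·f].

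| d | k | f = 0.5 | f = 1 |
|---|---|---|---|
| 1% | 2 | 1.000/0.995 = 1.005 | 1.01 |
| 5% | 2 | 1.000/0.975 = 1.026 | 1.05 |
| 5% | 3 | 1.025/0.975 = 1.051 | 1.10 |
| 10% | 3 | 1.050/0.950 = 1.105 | 1.20 |
| 15% | 3 | 1.075/0.925 = 1.162 | 1.30 |

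With k = 1 the ratio is 1.00. With f = 1 the formula reduces to 1 + d(k−1). That shortcut treats a share of subjects as a share of person-time, so it overstates the effect when leavers stop early.

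**Step 2: subjects first exposed in Study 116.** They were never selected on TEZ/IVA tolerance, so they dilute the effect. Suppose they are 10-50% of the 65, that is 5-27% of 121. For d = 5%, k = 3, f = 0.5, the Study 116/parent ratio is 1/1.051 = 0.951 before dilution. It becomes 0.951 to 0.964 after dilution, if intolerant first-exposed subjects contribute 5-50% of a full Study 116 follow-up. The dilution is small.

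**Step 3: mix of parent studies.** Use 56 and 65 as stand-ins for parent counts, with 24 and 8 weeks of parent treatment, and assume 10-33% of the 65 were not on TEZ/IVA.
- Study 113B share of parent TEZ/IVA person-time: 56×24 / (56×24 + 65×0.90×8) = 1344/1812 = 74%, up to 1344/(1344 + 65×0.67×8) = 1344/1692.4 = 79%.
- Study 113B share in Study 116, if all enter with equal follow-up: 56/121 = 46%.
- If the Study 115 AE rate were 1.25 times the 113B rate, mix alone gives a Study 116/parent ratio of 1.065 to 1.079. Combined with selection (d = 5%, k = 3, f = 0.5) it is 1.014 to 1.026, so Study 116 looks slightly worse.
- If it were 0.8 times, mix and selection together give 0.885 to 0.895.

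The mix can therefore cancel the selection effect or roughly double it.

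**Step 4: denominator, a separate matter.** If dosing days were used while events count through the TE period, counted time would exceed the denominator by 28/672 = 4.2% for a 96-week completer with full follow-up, and by 28/84 = 33% for one subject stopping at Week 12. For subjects who move to Part B or commercial drug after completing, SAP 9.1 ends participation at the Week 96 Visit, so little or no excess arises. Where it arises, the mismatch raises the rate.

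**The case against.** The strongest reply is that the display is descriptive, that no test or decision hangs on it, and that the primary assessment is the Study 116 Safety Set itself. That stands, and it limits the consequence.

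A reader might infer that Study 116 rates are bound to look lower, or that Study 116 excludes exactly the subjects who did not tolerate the drug. The documents support neither.
- Permanent discontinuation is a categorical bar, but other intolerance is left to the investigator. Protocol 8.1 also admits subjects with drug interruptions, including for raised transaminases, with the medical monitor's approval. Poor compliance is not intolerance.
- The downward direction needs a higher AE rate in those who did not roll over, and Step 3 shows that the study mix can reverse it.
- Percentages of subjects with an event, also planned, move the other way because follow-up is longer. At an illustrative 0.3 events per patient-year, 1 − exp(−0.3·weeks/52.18) gives 4.5% at 8 weeks, 12.9% at 24 and 42.4% at 96.
- The denominator question cannot be added to the selection effect: where follow-up after the last dose exists it pushes the rate up, and the SAP never ties dosing-day exposure to the AE rates.

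A rollover-only parent column is also a possible reading, since SAP 4 frames the plan around subjects who went on to enroll in Study 116. But SAP 10.3 states only one restriction, receipt of TEZ/IVA, and the listing rule in SAP 10.1 covers anyone dosed in either study. The wider reading is the natural one, though not an explicit one.

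Finally, replacing the parent column with rollover subjects would create its own distortion: AEs leading to permanent discontinuation in the parent study would be zero by construction. This is why the remedy adds a column pair and does not substitute one.

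**Conclusion.** The point holds as a matter of interpretation. The two columns are different populations, and exposure adjustment does not repair that, so the contrast mixes change over time with change of population. Selection alone would put the all-parent rate about 3-16% above the rollover subjects' own parent rate for d = 5-15%, k = 2-3 and half follow-up, or 5-30% with equal follow-up. All of these inputs are assumed; if few subjects failed to roll over, the effect is near zero (0.5-1% at d = 1%, k = 2). The net direction cannot be settled from the documents. The Study 116 safety summaries taken on their own are unaffected. This is an inexpensive improvement to the one comparative safety display, not a fault in the primary analysis.

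**What to change.** In SAP 10.3:
- Keep the all-parent TEZ/IVA column, label it as including subjects who did not roll over, and report how many did not enter Study 116 and why.
- Add a column pair: the parent-study TEZ/IVA rates of subjects who are also in the Study 116 Safety Set, and those same subjects' Study 116 rates, split by parent study. Under unchanged individual risk this pair gives a ratio of 1.00 within each parent study.
- Show subjects first exposed to TEZ/IVA in Study 116 separately.
- Footnote that AEs leading to permanent discontinuation are zero by construction in the rollover-only parent column, so for those rows only the all-parent column should be read.
- As a separate clarification, state one person-time denominator for every column that matches the period over which events are counted (the TE period).

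The cost is SAP wording, a wider table and a smaller parent denominator in the added column. No new data collection is needed in Study 116.
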